1.3 Detailed plan of investigation

1.3.1 Trial design

The trial will take the form of a prospective, pragmatic⁸, three-armed cluster randomised trial with an economic evaluation. Analysis will be on an ‘intention to treat’ basis. Participating practices will be randomised to one of three arms: (1) prescription of laxatives; (2) provision of standardised, non-personalised dietary and lifestyle advice; (3) provision of personalised dietary and lifestyle advice, with reinforcement.

A randomised controlled trial is the optimum design when evaluating behaviour change interventions. However, in this study, if the unit of randomisation was to be the individual patient, there would be a risk that health care professionals might provide elements of the dietary and lifestyle package to patients randomised to laxatives only. A solution to this problem is to ‘cluster randomise’ at the level of an entire practice, while collecting data about outcomes of care at the individual patient level. As patients within any one cluster are more likely to respond in a similar manner, such a design violates the assumption that the outcome for an individual patient is completely independent of that for any other patient. Therefore a cluster randomised design is not

as statistically efficient as a patient randomised design; it has lower statistical power than a patient-randomised trial of equivalent size⁹ and sample sizes need to be inflated to compensate for this (1.3.6).

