1.3.8.4 Synthesis of costs and outcomes

If there is not statistically and clinically significant evidence that one treatment strategy is superior to another in terms of health utilities or DFDs, a cost-minimisation framework will be used and the adoption of the less expensive strategies will be recommended. Similarly, recommendations for adoption will be made if one strategy appears to be more effective and less costly than its comparator(s). If one strategy appears to be more effective but more expensive than its comparator(s), estimates of incremental cost-effectiveness ratios will be generated and compared. A judgement will be required in a policy-making context to establish whether the additional benefits warrant the additional costs. In any case, results will be presented taking into account the issues of the generalisability of the results to other local settings.

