1.3.8.5 Sensitivity analysis

Issues of uncertainty in assumptions, methods and data, and of the generalisability of the results will be addressed in the sensitivity analysis, where the robustness of the results to any variations in key data inputs to the study will be tested. Moreover, a sensitivity analysis, taking into account of differences in resource use which are practically significant (i.e. potentially costly) but which have not been shown to be statistically significant, will be also be undertaken.

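### The economic adoption rules act on what appears better or cheaper, and do not carry the joint sampling uncertainty of costs and effects into the three-arm recommendation

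*Protocol*

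**What the plan says.** Section 1.3.1 randomises practices to three alternative strategies: laxatives, standardised advice and personalised advice. Section 1.3.8.4 gives rules for combining costs and outcomes:

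1. If no strategy is shown superior, statistically and clinically, on utilities or discomfort-free days, "a cost-minimisation framework will be used and the adoption of the less expensive strategies will be recommended".
2. On simple dominance: "recommendations for adoption will be made if one strategy appears to be more effective and less costly than its comparator(s".
3. On a trade-off, where a strategy appears better but dearer: "estimates of incremental cost-effectiveness ratios will be generated and compared". This rule ends in a policy decision: "A judgement will be required in a policy-making context to establish whether the additional benefits warrant the additional costs".

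Uncertainty is taken up in section 1.3.8.5. It names data as one source of uncertainty and describes a sensitivity analysis in which "the robustness of the results to any variations in key data inputs to the study will be tested". It adds an analysis of resource differences that could be costly but did not reach significance.

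The clinical analysis in section 1.3.7 fits practice as a random effect and promises interval estimates for differences between arms. Sections 1.3.8.4 and 1.3.8.5 make no matching statement for costs, ratios or the recommendation.

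**The concern.** Comparative cost-effectiveness is the commissioned question (section 1.1), so the rule that turns data into a recommendation matters. There are three weaknesses.

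- **Point-based triggers.** Rules 2 and 3 turn on what appears better or dearer. The only statistical test in section 1.3.8.4 is on effects, in rule 1. Costs have no counterpart there, and the correlation between cost and effect plays no part.
- **Non-significance read as equality.** Rule 1 recommends the cheaper arm whenever superiority is not shown. Section 1.3.8.2 itself expects that EQ-5D may be too insensitive in this population, so this route could well be taken. A strategy that appears better and dearer, but not significantly better, also fits both rule 1 and rule 3.
- **Open comparison order.** With three mutually exclusive strategies, each must be judged against the next best cheaper one, after dominated and extendedly dominated arms are removed. The text says only comparator(s).

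Varying inputs shows how the answer depends on unit costs or assumptions. It does not show how often the ranking would change in a repeat of the trial.

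**Working it through.** **The plan's own figure.** Inputs from section 1.3.6.3: effect 0.3 SD, power 90%, significance level 5% (taken as two-sided), ICC 0.04, 25 patients per practice.

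- Patients per arm before clustering: 2 × ((1.960 + 1.282) / 0.3)² = 233.5, so 234.
- Design effect: 1 + (25 − 1) × 0.04 = 1.96.
- Practices per arm: 234 × 1.96 / 25 = 18.35, so 19, or 57 in total. This reproduces the protocol.
- Effective patients per arm: 19 × 25 / 1.96 = 475 / 1.96 = 242.

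**Assumed inputs for the illustration.** The protocol gives no cost, QALY, SD or threshold. Assume, relative to laxatives: standardised +20 pounds and +0.004 QALY; personalised +100 pounds and +0.006 QALY; threshold 20,000 pounds per QALY.

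**Order of comparison.**

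- Standardised against laxatives: 20 / 0.004 = 5,000.
- Personalised against laxatives: 100 / 0.006 = 16,667.
- Personalised against standardised: (100 − 20) / (0.006 − 0.004) = 40,000.
- Net benefit (threshold × effect − cost): laxatives 0; standardised 80 − 20 = 60; personalised 120 − 100 = 20.

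Both ratios against laxatives fall under the threshold, yet standardised advice is best. If standardised advice were instead +40 pounds and +0.001 QALY, its ratio against laxatives would be 40 / 0.001 = 40,000. Personalised against standardised would then be 60 / 0.005 = 12,000, so standardised is extendedly dominated.

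**Sampling error.** SE of a between-arm QALY difference = SD × √(2 / 242). The table shows how often each arm had the highest net benefit in 200,000 simulated trials under the first set of values (cost SD 100 pounds, costs and effects uncorrelated, ICC 0.04 for both).

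| Assumed QALY SD | SE of difference | Laxatives | Standardised (truly best) | Personalised |
|---|---|---|---|---|
| 0.05 | 0.0045 | 17% | 56% | 26% |
| 0.10 | 0.0091 | 25% | 45% | 30% |
| 0.20 | 0.0182 | 29% | 39% | 32% |

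Cost SDs of 50 or 200 pounds barely change these figures.

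**The significance gate on the same values.** At the smallest SD, the true gain for standardised advice is 0.004 / 0.0045 = 0.89 standard errors, well short of 1.96. For personalised advice it is 0.006 / 0.0045 = 1.33. An estimate near either value would trigger rule 1 unless discomfort-free days differed significantly. The rule would then recommend the cheapest arm, laxatives (net benefit 0), although standardised advice has 60.

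**The case against.** - **The missing comparison is already an objective.** Objective 2 in section 1.2.1 asks for the cost-effectiveness of standardised against personalised advice. A reader might infer that all ratios are taken against laxatives, which would hide the 40,000. The text does not say so, and its wording is compatible with a full incremental analysis. This stands: the order is undefined, not wrong.
- **Uncertainty is not absent.** A reader might infer bare point estimates with no sampling uncertainty. That goes too far. Rule 1 is a significance gate, section 1.3.8.5 names data among the sources of uncertainty, and its analysis of non-significant resource differences presupposes some testing.
- **Clustering.** A reader might infer that economic intervals will ignore practices. They would then be 1 − 1/√1.96 = 29% too narrow if costs share the ICC of 0.04. Nothing says this will happen, and section 1.3.7 models practices for the clinical outcomes.
- **The ratio example may not be reached.** With gains this small, rule 1 would usually apply first. This is fair, but it moves the difficulty to rule 1 and does not remove it.
- **Rule 3 does not choose automatically.** It ends in a policy judgement, and section 1.3.8.2 shows costs and outcomes by arm, so readers can form any increment. This stands for rule 3, but rules 1 and 2 do end in recommendations.
- **Method detail belongs in an analysis plan.** This is true of the choice of bootstrap or model, and silence on that is no fault. The adoption rules, however, are fixed in the protocol.

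**Conclusion.** The point holds in a limited form. Section 1.3.8.4 fixes adoption rules that rest on what appears better and cheaper, or on the cheaper arm after a non-significant effect test. Section 1.3.8.5 describes input variation, which cannot stand in for the joint sampling error of costs and effects in a practice-clustered design. The undefined comparison order is a lesser gap, because objective 2 already implies the key contrast.

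No trial result can be recomputed, and the documents do not show that a wrong strategy will be chosen. The 5,000, 16,667 and 40,000 pounds, the 56% to 39% and the 29% all rest on assumed values. They show that the mechanism is real and that ranking uncertainty could be large. This is a cheap improvement to the analysis; it does not undermine the trial.

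**What to change.** In section 1.3.8.4, replace the triggers based on appearance and on non-significance with the following:

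- Order the three arms by mean cost, remove dominated and extendedly dominated arms, and report each remaining arm against the next cheaper one.
- Report net benefit for all three arms over a range of thresholds.
- Give intervals and the probability that each arm is best, from a method that keeps costs and effects together and respects practices. Examples are a two-stage bootstrap (practices, then patients) or a bivariate mixed model with practice effects.

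In section 1.3.8.5, keep the variation of inputs as an additional sensitivity analysis.

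The cost is a few sentences and slightly more programming, with no new data. The downside is that the recommendation carries a probability and is no longer a single verdict.

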1.3.8.5 Sensitivity analysis

Issues of uncertainty in assumptions, methods and data, and of the generalisability of the results will be addressed in the sensitivity analysis, where the robustness of the results to any variations in key data inputs to the study will be tested. Moreover, a sensitivity analysis, taking into account of differences in resource use which are practically significant (i.e. potentially costly) but which have not been shown to be statistically significant, will be also be undertaken.

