1.3.5 Assessment of outcomes

1.3.5.1 Outcome measures

The primary outcome, and the criterion upon which the sample size calculations have been based, is patient-reported condition-specific quality of life at three months post recruitment (1.3.5.2). Our preferred measure of quality of life is the constipation-specific PAC-SYM / PAC-QOL²⁵, which has been demonstrated to have good validity and reliability. However, this measure is not utility-based. For the purposes of the economic evaluation (1.3.8), a measure of the utility placed by patients on

their health state will be required. The condition-specific measure of quality of life will therefore be supplemented by the generic, utility-based EQ-5D^{26;27}.

Secondary outcomes will include: bowel movement frequency; the presence/absence of the other Rome criteria for constipation; patients' own perceptions of whether or not they are constipated; patient satisfaction with bowel function; adverse effects of treatment; relapse / re-consultation rates; fluid and fibre intake (Table 1).

In addition, the cost implications of the condition and its treatment (e.g. GP consultations, purchase of prescribed and over-the-counter medication) will be assessed, as part of the economic evaluation (Table 2; section 1.3.8).

Table 1 Outcome measures

Primary outcome	Measurement method	When	Where
Health-related quality of life	Postal questionnaire	At three months post recruitment	Participant's home
Secondary outcomes	Measurement method	When	Where
Health-related quality of life	Postal questionnaire	At six and twelve months post recruitment	Participant's home
Number of bowel movements per week	Self-completed structured diary + Postal questionnaire	Daily for 6 months At 12 months	Participant's home
Other Rome criteria: straining at defecation, stool consistency, perceived incomplete evacuation	Self-completed structured diary + Postal questionnaire	Daily for 6 months & for 1 week at 12 months At 12 months	Participant's home
Subjective perception of whether constipated; satisfaction with bowel function	Telephone interview + Postal questionnaire	At 3 months At 6 months & 12 months	Participant's home
Adverse events: abdominal pain, nausea, bloating, flatulence, diarrhoea	Self-completed structured diary + Postal questionnaire	Daily for 6 months & for 1 week at 12 months At 12 months	Participant's home

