1.3.6.3 Sample size

Participating practices will be randomised to one of three arms. In calculating sample size for cluster randomised trials³¹, it is necessary to take into account within-cluster variance, measured

by an intra-class correlation (ICC). Our experience in previous studies suggests that intra-class correlations of 0.05 for quality of life outcome are typical.

Preliminary analysis of data from the average-sized practices of one of the applicants suggests that there will be approximately 40 patients in such a practice meeting eligibility criteria (1.3.4). We recognise that patients in practices allocated to the diet and lifestyle arms of the trial may be reluctant to undertake a change to their diet or lifestyle and may therefore withhold consent to participate. It is in anticipation of this risk that we have made the assumption that only 30 out of 40 patients identified will agree to participate and that only 25 will provide follow up data for 12 months.

Our primary outcome is a continuous variable – score on a quality of life (QoL) scale. In the absence of detailed data on the distribution of QoL scores in our population, we can nonetheless specify the effect size that we wish to detect. We arbitrarily set this at 0.3 standard deviations on the condition-specific quality of life scale. Within the literature on quality of life assessment, there is a growing consensus³² that an effect size (i.e. change over time divided by standard deviation at baseline) of less than 0.2 represents a negligible change, an effect size of 0.2 up to 0.5 represents a 'small' effect, an effect size of 0.5 up to 0.8 represents a 'moderate' change and an effect size of in excess of 0.8 represents a 'large' change. These criterion values, which have been shown to be stable across a range of settings, have been established by reference to what clinicians and patients consider to be an 'important' difference – the emphasis is therefore on clinical rather than statistical significance. Our proposed effect size of 0.3 therefore represents the difference between the threshold values for 'small', 'moderate' and 'large' changes (0.5 – 0.2; 0.8 – 0.5).

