It is important to note that the LIFELAX trial is not a comparison of an intervention with placebo or with normal practice. Instead, there are three active treatment groups. It is not unreasonable to assume that we might observe at least a small change over time in symptom-related and quality of life outcomes in all of these treatment groups. What we are primarily interested in is whether one intervention offers a relative advantage over the others. For example, if the changes over time for the laxative and standardised diet and lifestyle interventions were 'small' by the established criteria set out above, but a 'moderate' improvement was observed in the individualised diet and lifestyle arms, we might reasonably conclude that this intervention offered a relative advantage.

For an effect size of 0.3, 90% power, a significance level of 5%, an intra-class correlation of 0.04, and the ability to recruit and retain 25 patients per practice, we therefore need a total of 57 practices (19 per arm).

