1.3.8.3 Resources data collected within the trial and costing methods

Costs to the National Health Service (NHS) will be estimated on the basis of the use of resources needed to implement the three proposed treatment strategies as well as those related to the subsequent use of services. Relevant costs include prescribed laxatives, consultations with GPs and nurses, and services related to the dietary and lifestyle interventions, such as the delivery of advice packages. The costs of preparing and delivering information materials and of training health care professionals in their use will also be estimated. These latter represent ‘start-up’ sunk costs, which would not be recurrent once the intervention is in place. Allowance against future savings will be made in the cost-effectiveness analysis for this initial investment.

Data on consultation rates and drugs prescribed will be collected through extraction of data from medical records of trial participants. Use of resources related to case management services and start-up costs will be gathered from the protocol, which will describe in detail how the dietary and lifestyle intervention will be delivered. Costs related to the use of medication and health services will be assigned using national published data for the United Kingdom^{24;34}.

Costs falling on the NHS will be supplemented with costs falling on patients themselves. These will be derived through telephone interviews, and will include information about the patients' purchase of over-the-counter laxatives and any other possible expenditure relating to the management of constipation (e.g. use of complementary medicine, travel costs). Where possible, participants will be asked to report costs and quantities separately.

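### The sensitivity analysis in 1.3.8.5 implies that non-significant resource-use differences are left out of the base-case costs, which 1.3.8.2 and 1.3.8.3 do not say; if they are, the less expensive strategy can be misnamed

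*Protocol*

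**What the plan says.** Four sections of the protocol's economic evaluation bear on the point.

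- **1.3.8.5 (sensitivity analysis)** first promises to test robustness to key inputs. It then adds a further sensitivity analysis to take account of "differences in resource use which are practically significant (i.e. potentially costly) but which have not been shown to be statistically significant".
- **1.3.8.3 (costing)** bases NHS costs on the resources needed to deliver each strategy, "as well as those related to the subsequent use of services". It lists prescribed laxatives and GP and nurse consultations among the relevant costs and sets no significance condition on any of them.
- **1.3.8.2 (type of study)** has costs tabulated by arm in the cost-consequence analysis, again with no significance condition.
- **1.3.8.4 (synthesis)** says that if no strategy is shown to be superior on utilities or discomfort-free days, "the adoption of the less expensive strategies will be recommended".

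Two other sections matter. In 1.3.5.1 the primary outcome, "the criterion upon which the sample size calculations have been based, is patient-reported condition-specific quality of life at three months", is what the trial is sized on. In 1.3.7, consultation and prescription rates at twelve months are among the outcomes for the mixed models, which are to yield interval estimates of the differences between strategies.

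**The concern.** A sensitivity analysis that brings in costly but non-significant differences has an obvious purpose only if the base case does not already contain them. If base-case costs were built from each arm's mean resource use, every difference would be in the total whatever its p-value. So 1.3.8.5 implies a significance filter on the base case that the costing sections do not describe.

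Such a filter would be a poor choice. Failing to reach p < 0.05 does not show that resource use is equal, least of all in a trial with no sample size calculation for consultations, prescriptions or cost. The estimated mean difference remains the best single estimate of the cost consequence, and its uncertainty belongs in an interval.

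At stake is the recommendation itself. In the cost-minimisation branch of 1.3.8.4, cost alone decides which strategy is recommended. Section 1.3.8.2 expects that the EQ-5D may be too insensitive to show differences in this population, so that branch could well be used.

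**Working it through.** **1. What the trial is sized for.** Inputs from 1.3.6.3: "For an effect size of 0.3, 90% power, a significance level of 5%, an intra-class correlation of 0.04", and 25 retained patients per practice. Sidedness is not stated; a two-sided test reproduces the plan's figure.

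- Patients per arm without clustering: 2 × (1.960 + 1.282)² / 0.3² = 233.5, rounded up to 234.
- Design effect: 1 + (25 − 1) × 0.04 = 1.96.
- Patients per arm with clustering: 234 × 1.96 = 458.6.
- Practices per arm: 458.6 / 25 = 18.35, rounded up to 19, so 57 in total.

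This matches the protocol. No cost SD, cost ICC or expected cost difference enters the calculation.

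**2. The sections side by side.** Sections 1.3.8.2 and 1.3.8.3 cost all listed resource use, without a test. Section 1.3.8.5 gives differences that fail a test a separate analysis. No sentence says which describes the base case.

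**3. How often a filter would drop a real difference.** All inputs here are assumptions except the size: 19 × 25 = 475 patients per arm. Differences are in SD units of the resource item, and a range of ICCs is shown because none is given for resource use.

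- SE = √(2 × (1 + 24 × ICC) / 475). At ICC 0.04 this is √(3.92 / 475) = 0.0908. At ICC 0.01 it is √(2.48 / 475) = 0.0723.
- Probability of missing a true difference d at two-sided 5% ≈ Φ(1.96 − d/SE); the opposite tail is negligible at d = 0.2.
- d = 0.2, ICC 0.04: Φ(1.96 − 2.20) = Φ(−0.24) = 40%.
- d = 0.2, ICC 0.01: Φ(1.96 − 2.77) = Φ(−0.81) = 21%.
- Over the wider range, d = 0.2 is missed 13% of the time at ICC 0 and 45% at ICC 0.05.

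**4. Whether this could change the named strategy.** Suppose one strategy costs a known 0.1 SD more to deliver and truly saves 0.2 SD in later service use, so it is cheaper by 0.1 SD. With the filter, it is named cheaper only if the estimated saving exceeds both 0.1 and 1.96 × SE. Without the filter, the estimate need only exceed 0.1.

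| ICC | Wrong strategy named, filter | Wrong strategy named, estimate always used |
|---|---|---|
| 0.01 | Φ((0.142 − 0.2)/0.0723) = 21% | Φ((0.1 − 0.2)/0.0723) = 8% |
| 0.04 | Φ((0.178 − 0.2)/0.0908) = 40% | Φ((0.1 − 0.2)/0.0908) = 14% |

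By symmetry the same figures apply to a strategy that is 0.1 SD cheaper to deliver but truly causes 0.2 SD more later use. The filter can therefore err for or against any arm.

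**The case against.** The strongest reply is that the filter is nowhere stated. Section 1.3.8.3, which defines the costing, has no significance condition, and neither does the word for cheaper in 1.3.8.4, where significance is applied to utilities and discomfort-free days. The sentence in 1.3.8.5 could also mean that costly but statistically uncertain items will be varied or removed to see whether conclusions hold. This stands to the extent that the filter is an inference. It does not remove the problem: the sentence speaks of taking these differences into account, not of removing them, and the base case stays ambiguous under either reading.

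The reply is also right that several stronger readings do not hold:

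- **That the base case is known to treat non-significance as no difference.** A reader may infer this from 1.3.8.5, but no section says it.
- **That the costs are biased against the advice arms.** Section 1.3.8.3 says "Use of resources related to case management services and start-up costs will be gathered from the protocol", so these items would escape a test while record-based items would not. But bias against the advice arms would also require that those arms save later resources. Section 1.3.3.1 lets their patients continue laxatives, so extra use could equally be dropped, which would favour them.
- **That no intervals are planned.** Section 1.3.7 plans practice-adjusted intervals for consultation and prescription rates. It does not extend them to total cost. Nor does the plan describe an interval around a filtered total, so there is none to criticise.
- **That cost always decides adoption.** Where a strategy is more effective and more expensive, 1.3.8.4 turns to incremental ratios and a policy judgement.

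Finally, records are to be abstracted for all participants (1.3.5.3.5), and 1.3.6.3 expects 30 per practice to consent. With 30 rather than 25, the 0.2 SD miss rate falls only modestly, from 40% to 37% at ICC 0.04 and from 21% to 16% at ICC 0.01.

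**Conclusion.** The point holds as an inconsistency with a conditional consequence. Section 1.3.8.5 implies that costly but non-significant resource-use differences stay out of the base case, while 1.3.8.2 and 1.3.8.3 describe costing that would include them. If the implied filter is followed, absence of significance stands in for absence of a cost difference in a trial sized on quality of life alone, and the strategy recommended as less expensive under cost-minimisation can be the wrong one, in either direction.

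The size is an illustration, not an estimate. It rests on 475 patients per arm, a normal approximation, a two-sided 5% test, a true difference of 0.2 SD and an assumed ICC for resource use. What does not depend on those inputs is that the two descriptions of the base case need to be reconciled before cost data are analysed.

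**What to change.** In 1.3.8.5, replace the sentence on non-significant resource-use differences with wording such as: *The base case uses the estimated mean difference for every costed resource item, whether or not it is statistically significant. Uncertainty in total cost and in cost-effectiveness is shown by intervals that allow for clustering by practice.* This brings 1.3.8.5 into line with 1.3.8.2 and 1.3.8.3 and extends to total cost what 1.3.7 already plans for consultation and prescription rates. A version restricted to statistically significant items may be kept, but only as a sensitivity analysis.

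The cost is a change of wording and slightly more analysis work. The resource items are already to be collected. Cost intervals will be wider than under a filtered total, which reflects the real uncertainty.
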